#### (h) Probable duration of study : one year

(i) Parameter/Variables to be measured: Age, sex, race, occupation, number of

warts, site of warts, response rate,

DLQI

- (j) Outcome measures : Response rate of warts to IL MMR and IL Vitamin D3
- (k) Statistical methods to be employed :
- a. **Data handling:** Data were entered in Microsoft Excel 2010 (Microsoft Corporation, Redmond, Washington, USA) and statistical analysis was done using Statistical Package for the Social Sciences 10.5 version (Chicago, Inc)
- b. Coding: Alpha numerical code was used
- c. **Monitoring:** Data was entered after every day of work and supervised by guide.
- d. Statistical analysis: will be conducted as per both per-protocol and intentionto treat population (defined as all enrolled patients to whom study drug will be given; with the last observation carried forward) basis using two sided tests.
  For *descriptive statistics*, percentage, mean, S.D., median, and minimum, maximum will be calculated along with graphical and tabular presentation.
  For *inferential statistics*, statistical methods that will be used are as follow
- Chi square test and Fisher's exact test to compare the categorical data between the groups.
- Paired t test for comparing normally distributed continuous variables (pretreatment and post treatment DLQI) at different time point within the groups.
- 3. Mann- Whitney U test to compare the not normally distributed variables (age,

duration of illness, size, number)

4. Kaplan–Meier curves to compare the response rate (complete, excellent, good or poor response) on each follow up visit (week 3, 6, 9, 12) between the groups.

Test of significance will be considered when value of  $p \le 0.05$ .

- (I) Ethical clearance : Will be obtained from the Institutional Review
   Committee (IRC), BPKIHS and Nepal Health
   Research Council (NHRC)
- (m) Permission to use copyright questionnaire/Proforma : N/A
- **11. For Intervention trial**
- a. Permission from Drug Controller of Nepal: not required
- b. Safety measure :will be applied
- c. Plan to withdraw : As per the decision of treating physician
- 12. Maintain the confidentiality of subject : Yes
- 13. References : attached
- 14. Whether available resources are adequate: adequate
- **15. Other resources needed** : not needed
- 16. Cost involved (Approx in NRS)
- a. Investigations :60,000 (approximate)
- b. Surgery :NA
- c. Drugs :64,500 (approximate)

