# **OBJECTIVES**

# **Primary Objectives:**

- 1. To determine the efficacy of IL MMR vaccine in the treatment of Wart
- 2. To determine the efficacy of IL vitamin D in the treatment of wart
- 3. To compare the efficacy of IL MMR vaccine and IL Vitamin D

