#### Statistical analysis

- Data handling: Data will be entered in Microsoft Excel 2010 (Microsoft Corporation, Redmond, Washington, USA) and statistical analysis will be done using Statistical Package for the Social Sciences 10.5 version (Chicago, Inc)
- 2. Coding: Alpha numerical code will be used
- Monitoring: Data will be entered after every day of work and supervised by guide.
- 4. Statistical analysis will be conducted as per both per-protocol and intention-to treat population (defined as all enrolled patients to whom study drug will be given; with the last observation carried forward) basis using two sided tests.

For *descriptive statistics*, percentage, mean, S.D., median, and minimum, maximum will be calculated along with graphical and tabular presentation.

For inferential statistics, statistical methods that will be used are as follow

- a. Chi square test and Fisher's exact test to compare the categorical data between the groups.
- b. Paired t test for comparing normally distributed continuous variables (pretreatment and post treatment DLQI) at different time point within the groups.
- c. Mann- Whitney U test to compare the not normally distributed variables (age, duration of illness, size, number)
- d. Kaplan–Meier curves to compare the response rate (complete, excellent, good or poor response) on each follow up visit (week 3, 6, 9, 12) between the groups.

Test of significance will be considered when value of  $p \le 0.05$ .

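### Response is compared at four visits and in two analysis sets at p ≤ 0.05, with none named as deciding, so the false-positive risk on MMR versus vitamin D exceeds 5% by an amount that depends on the unstated test

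*Combined protocol and SAP*

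**What the plan says.** The third primary objective is "To compare the efficacy of IL MMR vaccine and IL Vitamin D". The outcome measure in Summary item 10(j) is "Response rate of warts to IL MMR and IL Vitamin D3", with no time point and no response grade.

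The Statistical analysis section, repeated almost word for word in Summary item 10(k), sets out the comparison:

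- Item 4: "Statistical analysis will be conducted as per both per-protocol and intention-to treat population", the latter being everyone enrolled who received study drug, with last observation carried forward, "basis using two sided tests". Neither set is ranked.
- Item 4a: "Chi square test and Fisher's exact test to compare the categorical data between the groups", with no rule for choosing between the two tests.
- Item 4d: "Kaplan–Meier curves to compare the response rate (complete, excellent, good or poor response"), to be compared "on each follow up visit (week 3, 6, 9, 12) between the groups". No log-rank or other test is attached to the curves.
- One threshold covers everything: "Test of significance will be considered when value of" p ≤ 0.05.

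Table 3 (Operational definition) has four response grades. The Methodology section has both the patient and the physician rate response at each visit. No section names a deciding visit or set, or any multiplicity adjustment.

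**The concern.** The sample size rests on one comparison of two proportions at a two-sided 5% level. The analysis section offers several chances to answer the same question, each at that level. A significant result at one early visit, or in the per-protocol set only, could then be reported as showing that one treatment is better. If visits or sets disagree, no rule says which answer stands, so the choice can be made after the results are known.

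What is at stake is the reported error rate of the trial's main comparison. The sample size arithmetic itself is not in question.

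**Working it through.** **1. The plan's own figure.** Inputs from the Sample size section: p1 = 0.846, p2 = 0.40, so p = (0.846 + 0.40)/2 = 0.623; Z = 1.96 and 0.842.

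n = 2p(1 − p)(Zβ + Zα/2)² / (p1 − p2)² = 2 × 0.623 × 0.377 × 2.802² / 0.446² = 3.688 / 0.1989 = 18.54.

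This matches the plan (18.54, raised to 30 per group for loss to follow-up). It is one test at two-sided 5%.

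**2. Bounds for independent tests.** Four visits in one set: 1 − 0.95⁴ = 18.5%. Eight tests (four visits, two sets): 1 − 0.95⁸ = 33.7%. The same patients contribute at every visit and in both sets, so the tests are correlated and the true figures are lower.

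**3. Visit-by-visit tests, simulated with no true difference.** There were 30 patients per arm and 20,000 trials per row, with uncorrected chi-square tests on cumulative complete response. The documents give no response rates by visit, so the profiles are assumptions. So is the dropout used in the last column: 20% leave after the first response visit, and their last observation is carried forward in the intention-to-treat set.

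| Assumed response by weeks 3/6/9/12 | Any of four visits, one set | Any visit, either set |
|---|---|---|
| 8/25/45/60% | 15.3% | 19.8% |
| 10/30/50/70% | 16.1% | 21.2% |
| 5/15/28/40% | 13.4% | 17.0% |
| 10/25/40/50% | 14.6% | 18.8% |

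**4. Effect of the test, same profiles.**

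- Fisher's exact test throughout: 5–7% for four visits in one set, 9–12% over both sets.
- Fisher when an expected count is below 5, otherwise chi-square (an assumed rule; the plan gives none): 9.5–12.5% for four visits, 13.1–17.8% over both sets.

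**5. Sensitivity.** Other assumed profiles ending at 60–62%, with dropout of 10–38%, give 17.6–22.5% over both sets with chi-square if response is never lost, and up to 26.6% if it can fluctuate. With Fisher the range is 9.7–14.4%.

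**6. One log-rank test per set.** Two tests with correlation r give 1 − P(|Z1| ≤ 1.96 and |Z2| ≤ 1.96). With r assumed to be 0.8, 0.9 and 0.95, this is 7.8%, 7.0% and 6.5%. Simulation with assumed profiles gives about 6–8%.

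**7. Direction.** The alternative hypothesis is that MMR is better. A false finding in that direction is about half of each two-sided figure, against 2.5%: roughly 8.5–10.5% (chi-square, both sets), 4.5–6% (Fisher, both sets) and 3–4% (log-rank).

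**8. One named comparison.** One visit, one set and one test give 5% nominal. Simulated at the last visit in the intention-to-treat set, this is 4.9–5.4% with chi-square and 2.5–2.9% with Fisher.

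**The case against.** The strongest objection is that item 4d names Kaplan–Meier curves and no test. A Kaplan–Meier comparison is ordinarily one test over the whole of follow-up, so the four weeks may only mark when response is recorded. This stands: a test at every visit is a reasonable reading, helped by the words about each visit and by the chi-square and Fisher item, but the plan does not state it. On the log-rank reading the excess over 5% is small. It does not vanish, because two unranked sets remain and nothing says what happens if they differ.

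A reader might infer that the plan tests response four times and so carries a false-positive risk of 15–20%. The documents do not support that as a statement of fact. The figure belongs to chi-square tests at each visit, while item 4a also allows Fisher's exact test, which gives clearly lower values. The choice of test moves the result so much that no single figure can be given without it.

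A reader might also infer that the two sets are declared equal. The plan says only that both will be used; the ranking is absent rather than stated to be equal.

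**Conclusion.** The gap is real and should be corrected. The plan names no deciding visit or set and no adjustment, and applies one 5% threshold throughout, so the false-positive risk on the main comparison exceeds the 5% assumed in the sample size.

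Its size is conditional. Testing at each visit makes the excess moderate to large, depending on the test; one log-rank test per set makes it slight. All simulated values depend on the assumed profiles, and those over both sets also on the assumed dropout. The case for change does not depend on which reading is right, because no reading supplies a rule for conflicting results.

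The counts above use one response definition and one rater. The four grades and two raters in the plan leave room for further p values, so naming a visit and a set alone would not bring the risk down to 5%.

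**What to change.** In item 4, and in the matching text of Summary item 10(k), name one primary comparison tested once at two-sided 5%, fixing five things:

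- **Event:** complete response. The literature review shows that this is the grade behind the 84.6% and 40% in the sample size, although the 40% refers to injected target warts, whereas Table 3 also counts distant ones.
- **Rater:** one, for example the physician assessment.
- **Visit:** one, for example week 12, the last listed in item 4d. If the first session is at week 0, the fifth of five three-weekly sessions falls at 4 × 3 = week 12, so a week 12 assessment may not reflect it. The investigators should weigh this when choosing the visit.
- **Set:** intention-to-treat.
- **Test:** one named test.

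Present the other visits, grades and ratings and the per-protocol set as supportive estimates with confidence intervals and no significance claim. State that the primary comparison decides if they disagree. If the Kaplan–Meier curves are kept, say whether a log-rank test goes with them and that it is supportive.

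If all four visits must carry claims, a threshold of 0.05/4 = 0.0125 in one named set keeps the risk at or below 5% (1 − 0.9875⁴ = 4.9% if independent). That is stricter than the level used for the sample size and would cost power.

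The cost of the main fix is a few sentences, with no extra patients or data. The downside is that an early-visit or per-protocol p value can no longer be claimed as proof.

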# ANNEXURES

### Department of Dermatology and Venereology

### **BPKIHS**, Dharan

### Proforma for Wart patients

SN:	Group:	OPD/Inpatient no:	Date:			
Name	e					
Age (years): Sex:						
Race/ethnicity:						
Education:		Occupation:				
Address:		Phone no.				
History:						
1) Duration of w	art:	2) Type of wart:				
3) Site	of lesions:	Scalp/Face/Neck/Trunk/Upper	extremities/Lower			
Extremities/Palr	ns/soles/finger/toes					
4) Number of Le	sions at presentatior	1:				
5) Size of lesion:						
6) Progression o	f lesion: Gradual/Rap	bid/Stable/ Regressing				
7) Any associate	d Symptoms:					
	Pruritus: none/ mild,	/ moderate/ severe				
	Pain: none/ mild/ mo	oderate/ severe				
	Burning sensation: n	one/ mild/ moderate/ severe				
8) Associated pe	rsonal Systemic illne	ss: Yes/No				
If yes: HIV/ Diab	etes/ Asthma/ Allerg	ic skin disorders/ Convulsion/ bone	pain/ muscle weakness			
9) Pregnant/ lac	tating mother: Yes/N	Io/ NA				
10) Taking any o	ther drugs: Yes/No					
If yes: Corticoste	eroids/ Immunosupp	ressive/ Others				
11) Past treatme	ent taken: Yes/ No					
If yes: Self-ca	re (Herbs/ Drugs/ Bo	ught from pharmacy)				
Traditio	nal (Traditional beak	ar/Herbalist/Other)				
Fractional (Fractional nealer/ Herbalist/ Other)						
Improve	Seek medical help or treatment (Topical/ Systemic/ Both/ Surgical)					
Timo cin	anent. worse/ NO/ N					
Time Sin						

Reason for treatment:

# Treatment given: IL MMR/ IL Vitamin D

# Response to treatment

Number	Date	Percentage		Percentage	Side effects	Remarks
of visits		decrease	from	decrease	(nain redness edema Infection scarring	(Vitamin
		haseline		from last visit	ulcer nigmentary changes flu like	
		baseline			symptoms anaphylavis confusion	20 dave
					symptoms, anaphylaxis, comusion,	20 uays
					polyuna, polyupsia, anorexia, nausea,	diter 3
					vomiting, muscle weakness, bone pain,	VISIT, I
					altered sensorium)	month
						after last
						dose)
1 st						
2 nd						
ard						
3.~						
4 th						
5 th						

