Measles, Mumps Rubella (MMR) vaccine is included in immunization schedule so pre-sensitization skin test is not needed as all patients are expected to be immune. In 1989, monovalent measles vaccine was introduced in Nepal for vaccination of infants at age nine months. In 2013, measles-rubella (MR) vaccine was introduced into the national routine immunization schedule and replaced monovalent measles vaccine. The presence of three different antigens in MMR

increases the sensitivity to the injected antigen and decreases the likelihood of anergy. Side effects of MMR include pain during injection, flu-like symptoms, pruritus and burning sensation.

Intralesional (IL) vitamin D is a novel addition to therapies in warts as it is a simple, effective, well-tolerable, and inexpensive method with negligible local and systemic side effects

Side effects of Vitamin D3 include transient mild to moderate pain, edema at the site of injection, resolving within 1 week mild erythema. Further it would be safer to measure serum vitamin D and calcium levels before and after intralesional vitamin D treatment to prevent possible hypervitaminosis D.

Vitamin D3 acts on the principle of immunotherapy by stimulating cell-mediated immunity In addition, it is also claimed to regulate epidermal cell differentiation and proliferation and may modulate cytokine production through its action upon vitamin D receptors(VDRs). VDRs are present in the keratinocytes, melanocytes, fibroblasts, and immune system cells of the skin. Activation of Toll-like receptor (TLR) of human macrophages up-regulates the expression of vitamin D receptor and vitamin D1- hydroxylase genes, leading to induction of the antimicrobial peptide like thymic stromal, lymphopoietin and cathelecidin.  It also reduces the synthesis of IL1a and IL6 resulting in decreased inflammation. VDR activators (VDRAs) have been shown to inhibit cell replication and have immunomodulatory properties.

It is supposed that combining intralesional immunotherapy with a destructive treatment method might enhance the efficacy, shorten the treatment duration, and reduce the possible side effects.

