Mohamad	Alexandria Main	Quasi	100	Plantar	82%
NS et al,	University Hospital,	experimenta		wart	
2013 	Egypt	l trial			
Shah A et al,	NHL Municipal	Prospective	50	Common	72%
2016 	Medical College,	study		warts	
	Ahmedabad,				
	Gujarat, India				
Raju J et al,	Mysore Medical	Prospective	27	Common	70.4%
2016 	College &	study		warts	
	Research Institute,				
	Mysore, India	-			
Rohit V et al,	Chalmeda Anand	Case-	50	Common	72%
2017**	Rao Institute of	control		warts	
	Medical Sciences,	study			
	Telangana, India.				22.424
Chauhan PS	Dr.R.P. Govt.	Prospective	51	Common	82.4%
et al, 2017 	Medical College,	study		warts	
	Kangra (Tanda),				
	Himachal Pradesh,				
	India				

Table 1: Comparison of different studies on IL MMR in warts

Again in 2015, **Nofal et al** conducted a similar study in recalcitrant wart where they included sixty-five patients. Recalcitrant warts were defined as warts persistent for more than two years despite treatment with at least two different modalities. Distant warts were defined as warts at different anatomic sites away from the treated wart. Complete clearance of the lesions was observed in 41 patients (63%), partial response in 15 patients (23%), and no response in nine patients (14%). Complete response was demonstrated in 74.5% of those presenting with distant warts. Side effects were mild and insignificant in the form of pain during injection, itching, erythema, and edema at the site of injection and flu-like symptoms. Recurrence was detected in two patients only

Similarly in a study conducted by **Naseem, Aamir** in 2013 there were total 170 patients and final efficacy came as 81.3% which shows that a large number (122) of patients show complete response to the MMR vaccination.

**Nagat Sobhy Mohamad, et al** observed that the response of the target wart, MMR- treated group showed a significantly higher rate of complete clearance compared with the control group (82% versus 0% respectively). The rate of partial response was 6% versus 30%, and the rate of no response was 12% versus 70%, respectively. Regarding the response of untreated distant warts, the MMR-treated group showed 86.9% complete and 13.1% partial clearance of the warts whereas the control group showed 100% no response.

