# Secondary Objective:

- To determine the clinical and demographic profile of patients with different types of warts visiting Dermatology outpatient department of BPKIHS
- 2. To determine the side effects of IL MMR vaccine and IL Vitamin D in treatment of wart
- 3. To determine Dermatology life quality index (DLQI) in wart patients.

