### **Exclusion criteria**

- 1. Patients under any systemic or topical treatment of warts for the last 4 weeks
- 2. Patients with a past history of an allergic response to MMR or any other vaccine or Vitamin D
- 3. Patients with current acute febrile illness or any bacterial infection
- 4. Immunosuppressed patients
- 5. Pregnant or lactating women
- 6. Patients having a past history of asthma, allergic skin disorders or convulsions
- 7. Patients with keloidal tendency
- 8. Patient refusal for consent
- 9. Treating physician's decision to give other modality of treatment
- 10. Patients with hypervitaminosis D, muscle weakness, bone pain, altered sensorium

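### The per-visit side-effects prompts omit pruritus and burning sensation, two of the four MMR effects the protocol names, so these may be under-recorded

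*Combined protocol and SAP*

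**What the plan says.** Secondary objective 2 is "To determine the side effects of IL MMR vaccine and IL Vitamin D in treatment of wart".

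The Introduction states the expected effects of each agent. For MMR: "Side effects of MMR include pain during injection, flu-like symptoms, pruritus and burning sensation". For vitamin D3: "Side effects of Vitamin D3 include transient mild to moderate pain, edema at the site of injection, resolving within 1 week mild erythema". The literature review of intralesional MMR reports itching again, in the 2015 study of recalcitrant warts: "Side effects were mild and insignificant in the form of pain during injection, itching, erythema, and edema at the site of injection".

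The data are collected on the Proforma in the Annexures. Item 7 of the history grades three symptoms at entry on a four-point scale from none to severe: pruritus ("Pruritus: none/ mild" and so on), pain and burning sensation. The Response to treatment table, for visits 1 to 5, has a side-effects column with a bracketed list of prompts beginning "nain redness edema Infection scarring". It continues with ulcer, pigment change, flu-like symptoms and anaphylaxis, then nine general symptoms from confusion to altered sensorium.

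Under Methodology, the text after Group B says that immediate and late adverse effects of both agents are to be evaluated after every treatment session. It gives no method of eliciting them.

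**The concern.** The protocol names pruritus and burning as MMR effects and treats both as worth grading at baseline. The form that staff complete at each treatment visit then does not ask about them. Symptoms that are prompted tend to be recorded more completely than those left to be volunteered.

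The estimate at stake is the side-effect profile of MMR under secondary objective 2. A report of little or no pruritus or burning could mean that patients had none, or that nobody asked, and the data could not separate the two. If the arms are set side by side, the gap could make MMR look better tolerated, provided these symptoms really are commoner with MMR.

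A smaller point belongs with it. Pain is prompted at each visit but without a grade, and pruritus and burning do not recur at all. The form therefore cannot show whether any of the three has worsened from its graded baseline value.

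**Working it through.** The plan gives no figure on this point to reproduce. The check is a match of named effects against the prompt list, followed by an illustration of size.

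**1. Effects named against effects prompted**

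| Effect | MMR, Introduction | MMR, 2015 study in the literature review | Vitamin D3, Introduction | On the visit list |
|---|---|---|---|---|
| Pain | yes | yes | yes | yes |
| Flu-like symptoms | yes | yes | no | yes |
| Pruritus / itching | yes | yes | no | **no** |
| Burning sensation | yes | no | no | **no** |
| Erythema / redness | no | yes | yes | yes |
| Oedema | no | yes | yes | yes |

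- MMR, Introduction only: 2 of 4 prompted.
- MMR, with the erythema and oedema of the 2015 study added: 4 of 6 prompted.
- Vitamin D3, Introduction: 3 of 3 prompted.
- Vitamin D3, with the three symptoms named beside hypervitaminosis in the Exclusion criteria ("Patients with hypervitaminosis D, muscle weakness, bone pain, altered sensorium"): 6 of 6 prompted.

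On either MMR count the missing items are the same two.

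**2. Whether another record fills the gap**

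- Item 7 of the Proforma covers pruritus and burning, but only at entry.
- The Follow Up table (visits 6 to 8) has columns for percentage decrease, recurrence and remarks, and none for side effects.
- The first DLQI question touches on itch and burning. It is asked only before treatment and at the end of follow-up (Quality of Life section), and it concerns the skin problem rather than the injection.

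None of these captures the two symptoms session by session.

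**3. Possible size**

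Inputs: 30 patients per arm (Sample size section); r, the true proportion of MMR patients with pruritus or burning; c, the proportion of those whose symptom is written in without a prompt. The documents give neither r nor c, so both are assumptions. The number missed is 30 × r × (1 − c).

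| r (assumed) | Patients affected | Missed, c = 0 | Missed, c = 0.5 | Missed, c = 1 |
|---|---|---|---|---|
| 0 | 0 | 0 | 0 | 0 |
| 0.05 | 30 × 0.05 = 1.5 | 1.5 | 0.75 | 0 |
| 0.10 | 30 × 0.10 = 3 | 3 | 1.5 | 0 |
| 0.30 | 30 × 0.30 = 9 | 9 | 4.5 | 0 |

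The range is 0 to 9 of 30. It is set by the assumptions, and the documents do not narrow it.

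**The case against.** The strongest case on the other side has five parts.

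- **The column is a free entry.** The Methodology does not confine adverse effects to the printed list, and there is a Remarks column alongside, so itching or burning can be written in. This stands. It is why the claim is that they may be under-recorded, not that they will be. Even so, the prompts are the only stated guide to what is asked.
- **One form serves both arms.** The two prompts are missing for vitamin D3 as well. This stands: a bias in favour of MMR needs these symptoms to be commoner with MMR, and the only support for that is that the Introduction names them for MMR alone.
- **No comparison of side effects is specified.** The objective is to determine them; comparison appears only in the efficacy objective. A between-arm test would rest on the generic line on chi-square and Fisher tests for categorical data. This stands, but under-recording would still damage the MMR estimate on its own.
- **Baseline pain is already graded.** A reader might infer that wart pain at entry cannot be separated from treatment pain at all. That goes too far: patients with no pain at entry can be identified from item 7, and the MMR effect named is pain during the injection itself. What remains is that worsening cannot be read from an ungraded entry.
- **The form was read by a program and its text is garbled.** However, the list reads through to its closing bracket, so a lost item is unlikely. A glance at the printed form would settle it.

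**Conclusion.** The omission is real, and the change is a cheap improvement to the form. The visit list prompts for two of the four MMR effects in the Introduction (four of six on the wider count) and for every effect named for vitamin D3. Pruritus and burning may be under-recorded as a result. The primary objectives and the sample size are untouched.

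A reader might go further and infer that MMR side effects are under-counted in the comparison of arms by a definite number of percentage points, for example by combining an assumed pruritus rate with the injection-pain rates of 36% and 60% in the literature review. The documents do not support that. No rate of pruritus or burning is given, and an overall rate of any side effect is not an endpoint of the plan. The study with 60% pain reports no other adverse effect, and the summary of the study with 36% pain adds only flu-like symptoms in 4%. Another MMR study reports injection-site pain alone. Itching appears in one study summary and burning in none. Those studies may not have asked, but a rate of zero cannot be excluded. The under-count could also be zero if every symptom is volunteered.

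**What to change.** Add pruritus and burning sensation to the side-effects column of the Response to treatment table, for both arms. At each visit, record pain, pruritus and burning on the scale already used in item 7 of the Proforma, so that a new or worsened symptom can be told apart from one present at baseline. Report injection pain as its own item, separate from pain in the wart.

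The cost is two added entries, one reused scale and a few seconds more per visit. The reported side-effect rate may rise. The change needs to be in place before the visits take place, because symptoms not asked about at a visit cannot be reliably recovered later.
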